6. EFFICACY ANALYSIS

Efficacy results will be summarized for the target mTNBC Population, mBC Population and mUC Population. In addition, selected efficacy data will be summarized separately for each cancer type populations including SCLC, NSCLC, CRC, EGC, EMC and PDC. Formal statistical hypothesis testing will not be performed. Descriptive statistics, data summaries and graphical methods will be used to assess the efficacy of IMMU-132.

The primary endpoint will be the objective response rate (ORR) [PR+CR], with responders requiring a confirmatory response assessment no sooner than 4 weeks after the criteria for response are first met. Assessment of tumor response is based upon on-site readings by local radiologists, using RECIST 1.1 for all populations. Response rates will be additionally provided for the Target mTNBC Population and Per-Protocol Population (specific to mTNBC).

CCI [REDACTED] tumor scans were additionally assessed by independent central review (ICR) for mTNBC patients; however, this is not done for other cancer populations. For mTNBC population, an ICR was conducted for tumor scans from patients who achieved an objective response by local radiologists or at least 20% reduction of their locally determined target lesions. Local vs ICR assessments at each response time point and overall will be compared to determine concordance of local vs ICR best overall results. An imaging scans time point will be presented graphically for the Target mTNBC Population, whether tumor CT scans results were collected within allowed time windows at each of the imaging time points (based on 8 weekly imaging allowed by protocol and collection windows for study time points that were nominally within $\pm 10\%$), based on available data.

Secondary efficacy endpoints will include time to response (TTR), duration of response (DOR), clinical benefit rate (CR+PR+SD [stable disease] ≥ 6 months), progression-free survival (PFS), and overall survival (OS). DOR, PFS, and OS data will be analyzed via Kaplan-Meier method and 95% CI from Brookmeyer and Crowley method with log-log transformation. TTR will be summarized by descriptive statistics, whilst clinical benefit rate will be presented as a response rate along with ORR.

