6.1. Best Overall Response

Response will be determined using RECIST 1.1 criteria, and summarized by the best overall response (BOR) using the following hierarchical order: CR, PR, SD, PD, Not evaluable and Not assessed. CR or PR will require a confirmation scan.

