6.6. Duration of Response

Among responders (patients who have a best response of PR or CR), DOR will be calculated as the date of the first evaluation showing documented PR, or CR to the date of the first PD or Death. $DOR = (\text{Earliest Date of Progression or Death} - \text{Date of First PR/CR} + 1) / 30.4375$. For patients not progressing, censoring rules apply. DOR censoring rules are presented in [Table 4](#).

Table 4: Guidelines for Response Assessment and Censoring for Analysis of Duration of Response

Guidelines for Progression Assessment and Censoring for Analysis of Duration of Response			
Condition	Case	Outcome	Date of Progression or Censoring
Objective PD or Death occurred	At or between scheduled assessments or prior to missing 2 scheduled successive assessments	PD / Death	Date of objective PD or Death
	Progression or Death after missing 2 or more scheduled successive assessments	Censor	Date of last adequate response assessment
No objective PD or Death occurred	Initiated other treatment	Censor	Date of last adequate response assessment prior to starting other treatment
	Lost to follow-up	Censor	Date of last adequate response assessment
	Data cutoff	Censor	Date of last adequate response assessment

Abbreviations: CT = Computed tomography, MRI = Magnetic resonance imaging, PD = Progressive disease.

If the onset of response requires evaluations at different times (ie, chest CT on 1 day, abdomen and pelvic MRI several days later) the last measurement date should be used. For progression based on the sum of target lesion measurements at different times (ie, chest CT on 1 day, abdomen and pelvic MRI several days later) the last measurement date should be used. For progression based on new or nontarget lesions, if these are equivocal at 1 assessment and later considered unequivocal progression, the earliest date when progression was suspected should be used. If progression occurred after 2 or more scheduled successive response assessments were missed or inadequate, the outcome will be censored at the last prior adequate assessment. Adequate response assessment is defined as a response assessment other than "not assessed" or "not evaluable" for the determination of duration of response. If objective evidence of progression has not occurred and the patient is either lost to follow-up, died, a new treatment is initiated, or data cut-off occurs, then the outcome will be censored at the last prior adequate assessment.

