6.8. Other Analyses Related to Efficacy

[figure not shown]
Waterfall plots of the percent change from baseline in target lesion measurement will be presented.

Swimmer plots of onset to response and duration of response will be presented. The plot will include only CR and PR patients distinctly color coded; onset of response, response ongoing status will be marked at the end of the plot indicating 1) DOR is stopped by PD or death, 2) DOR is censored due to missing 2 or more scheduled, initiated of other treatment or loss to follow-up; and 3) DOR is ongoing (censored but not due to reasons listed in 2).

Example of swimmer plot:

Example of waterfall plot:

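### SAP 6.6 both counts and censors a responder's death without documented progression; the last sentence under Table 4 should be brought into line with the table

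*SAP*

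**What the plan says.** Four places treat a responder's death as ending the response:

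- **Definition (SAP 6.6).** DOR runs from the first evaluation "showing documented PR, or CR to the date of the first PD or Death".
- **Formula (SAP 6.6).** The end date is the earlier of progression and death.
- **Table 4, first row.** The outcome is PD or death, on its own date, when it falls "At or between scheduled assessments or prior to missing 2 scheduled successive assessments".
- **Swimmer plot (SAP 6.8).** The first end-of-bar group is "DOR is stopped by PD or death". The censoring reasons in the second group are missed assessments, other treatment and loss to follow-up. Death is not among them.

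Table 4 censors a death in one case only: when two or more successive assessments were missed beforehand. Its other censoring rows apply under the condition "No objective PD or Death occurred".

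The closing sentence of the text under Table 4 says something else. For a case with no objective progression it reads: "patient is either lost to follow-up, died, a new treatment is initiated, or data cut-off occurs, then the outcome will be censored". The censoring date is that of the last earlier adequate assessment.

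Protocol Appendix 4 ends the duration of response at objectively documented recurrence or progression and does not mention death.

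**The concern.** Two programmers working from the same SAP could give the same patient a different status and a different time. One would follow the definition and Table 4, the other the closing sentence. DOR is analysed by Kaplan-Meier (SAP 6), so the choice changes the estimate. Death soon after a response is unlikely to be unrelated to prognosis. Treating it as uninformative censoring therefore tends to flatter the curve.

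DOR is planned for the Target mTNBC Population and for every other cancer-specific population (SAP 4.4, Tables 1 and 2). The visible plan has no second DOR analysis that would expose the choice: Table 1 lists sensitivity analyses for ORR, PFS and OS only.

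**Working it through.** The plan states no figure on this point, so there is none to reproduce. The check compares the text, follows one patient through both rules, and then gauges the size under stated assumptions.

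**1. Where the rules differ**

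| Responder's death without objective PD | Definition, formula, Table 4 | Last sentence under Table 4 |
|---|---|---|
| Fewer than two successive assessments missed | Event on date of death | Censored at last adequate assessment |
| Two or more successive assessments missed | Censored at last adequate assessment (Table 4) | Censored at last adequate assessment |

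The conflict is confined to the first row. The closing sentence cannot be read as covering only the second. The missed-assessment rule stands two sentences earlier and speaks of progression, and the word for death in the closing sentence carries no such condition.

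**2. One assumed patient**

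Scans every 8 weeks on days 57, 113 and 169. First PR on day 57, confirmed on day 113 (at least 4 weeks later, as SAP 6 requires). Death on day 200 without PD. The next scan would fall on day 169 + 56 = 225, so none was missed.

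- Definition, formula and Table 4: event at (200 − 57 + 1)/30.4375 = 144/30.4375 = 4.73 months.
- Closing sentence: censored at (169 − 57 + 1)/30.4375 = 113/30.4375 = 3.71 months.

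Under the closing sentence this patient is censored for a reason outside the second swimmer-plot group. The third group takes all other censored cases, so the plot would show a dead patient's response as ongoing.

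**3. Size at 9 months**

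Inputs from the documents: confirmation is required ("CR or PR will require a confirmation scan", SAP 6.1) at 4 to 6 weeks, then scans run every 8 weeks (Protocol 3), with "collection windows for study time points that were nominally within" ±10% (SAP 6).

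Assumptions: exponential time from the confirmatory scan, with median 4 to 12 months; a share f of first events are deaths without PD; PD is dated at the next scan. The 9-month landmark is also my choice, not the SAP's. Simulation with 200,000 responders per setting gives:

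| f | Rise in Kaplan-Meier DOR at 9 months if deaths are censored |
|---|---|
| 5% | 1.3 to 1.7 points |
| 10% | 2.7 to 3.4 points |
| 20% | 5.7 to 7.1 points |

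Hand check: in continuous time, with deaths a constant share f of the hazard, a curve at S becomes S^(1 − f). At S = 0.50:

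- f = 5%: 0.50^0.95 = 0.518, a rise of 1.8 points;
- f = 10%: 0.50^0.90 = 0.536, a rise of 3.6 points;
- f = 20%: 0.50^0.80 = 0.574, a rise of 7.4 points.

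These are of the same order as the simulated values.

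**4. The median is a poor gauge**

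PD is seen only at scans, so the median moves in steps. On a strict 8-week grid with underlying medians of 6, 8 and 10 months, it did not move when such deaths made up 5–10% of the event hazard. In a very small sample it can even shorten. Take three patients: a death at 6.0 months with last scan at 5.0, PD at 5.5 and PD at 8.0.

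- Death as event: the curve is 2/3 after 5.5 and 1/3 after 6.0, so the median is 6.0.
- Death censored at 5.0: two patients are at risk at 5.5, the curve falls to 1/2, and the median is 5.5.

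**The case against.** **The governing rule can be identified.** SAP 6.6 says that the DOR censoring rules are those in Table 4, and the definition, formula and 6.8 agree with it. This stands as guidance on which way to repair the text. It does not remove the conflict, because the opposing sentence belongs to the text that explains that same table.

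**The closing sentence is nearer to the protocol.** Appendix 4 names only progression, and the January 2020 protocol revision, later than SAP version 3.0 of February 2019, still has that wording. This stands in part: the SAP should say which definition is used. It does not make 6.6 consistent.

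**Little depends on it.** "Formal statistical hypothesis testing will not be performed" (SAP 6), and DOR is a secondary endpoint. This stands and limits the weight of the point.

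**The figures depend on the model.** They do. The model keeps 8-weekly scans throughout, whereas Protocol 6.7 puts patients who have not progressed on 3-monthly imaging after treatment. Shifts in the median vary with how the scan windows are modelled, so I give no range for them.

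**A reader might infer that the reported DOR is inflated.** The documents do not support that. They do not show which rule was programmed. Parts of SAP 6.9 and Section 11 are redacted, and SAP 10 refers to a separate data handling and programming document, so the rule used may be recorded there.

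**Conclusion.** The contradiction is real and can be seen within a single section. It concerns responders who die without objective progression before two successive assessments are missed. For them the closing sentence changes both status and time, and usually leaves Kaplan-Meier DOR unchanged or longer.

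The true size is unknown, because the documents give no count of such deaths. Roughly 1 to 7 percentage points at 9 months is what the assumed model yields for shares of 5–20%. It is not an estimate for this trial.

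It would go too far to conclude that the median DOR is overstated by some percentage, or that the efficacy results as a whole are in doubt. ORR and OS do not use this rule, no test or error rate depends on it, and the sentence stands under Table 4 alone and does not govern PFS. The point should be fixed, but it does not threaten the trial's main results.

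**What to change.** 1. State in SAP 6.6 that Table 4 governs DOR events and censoring, and replace the closing sentence with wording such as:

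   *If a responder has had neither objective progression nor death, and is lost to follow-up, starts a new treatment or reaches data cut-off, DOR is censored at the last adequate assessment (the last one before the new treatment, where one was started). Deaths are handled as in Table 4.*

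   Deleting only the word for death would not be enough, since a dead responder without PD could still meet the data cut-off condition. Make no other change to Table 4. In particular, objective progression after a new treatment stays as the table has it.
2. Confirm that the DOR derivation and the swimmer plot follow Table 4, and re-run them if they do not.
3. Report, for each population, the number of responders' deaths affected.
4. State that the SAP definition of DOR is the one used, since Protocol Appendix 4 does not mention death.

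Cost: a few lines of SAP text, a check of one derivation with a possible re-run, and one count per population. The protocol need not be amended. DOR may come out slightly less favourable if the contradicting sentence had been programmed.

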6.7. Time to Response

[figure not shown]
Time to response is defined as the time from the first dose to the first documentation of response (PR or CR).

6.8. Other Analyses Related to Efficacy

[figure not shown]
Waterfall plots of the percent change from baseline in target lesion measurement will be presented.

Swimmer plots of onset to response and duration of response will be presented. The plot will include only CR and PR patients distinctly color coded; onset of response, response ongoing status will be marked at the end of the plot indicating 1) DOR is stopped by PD or death, 2) DOR is censored due to missing 2 or more scheduled, initiated of other treatment or loss to follow-up; and 3) DOR is ongoing (censored but not due to reasons listed in 2).

Example of swimmer plot:

Example of waterfall plot:

6.9. Sensitivity Analyses

CCI

Analyses based on the Per-Protocol Population will be performed for ORR, PFS, and OS for the Target mTNBC Population.

Sensitivity analyses will only be conducted for the Target mTNBC Population, but not planned for other cancer-specific analysis population.

CCI

CCI

CCI

CCI

CCI

7. SAFETY ANALYSIS

Safety will be assessed for the Target mTNBC Population, mBC Population, mUC Populations and the Overall Safety Population. Data will be presented in terms of AEs, laboratory data, ECG data, and vital signs.

7.1. Adverse Events

Treatment-emergent adverse events (TEAEs) are defined as any AEs that begin or worsen on or after the start of study drug through 30 days after the last dose of study drug. All AEs will be coded using Medical Dictionary for Regulatory Activities (MedDRA) Version 20.0 unless otherwise specified. The severity will be graded based on the National Cancer Institute's (NCI) Common Terminology Criteria for Adverse Events (CTCAE) Version 4.03. All AEs will be listed. Only TEAEs will be summarized and will be referred to as AEs hereafter. Timing of AEs and concomitant medications will take account of the date and the time of the AE or concomitant medication.

The frequency and severity of AEs will be tabulated by MedDRA SOC and PT. For this purpose, an AE that occurs more than once within each patient will be counted only once (at the worst CTCAE grade and relationship category). Adverse event tables will be sorted by SOC frequency and within each SOC, the PTs will be sorted by decreasing frequency for the total IMMU-132 treated patients' column reported in each table.

Additional by-patient listings will be provided for AEs leading to on-treatment death, serious AEs (SAEs), and AEs leading to discontinuation of treatment (excluding AEs leading to death).

Tables summarizing the incidence of AEs will be generated for each of the following:

1. Overall summary of AEs
2. All AEs by SOC and PT
3. Most common AEs (defined as $\geq 10\%$ of the total number of patients) by PT
4. Grade 3 or higher AEs by SOC and PT
5. AEs by SOC, PT, and grade; columns for: any grades; grade 3, grade 4, grade 5
6. Treatment-related AEs by SOC and PT
7. Treatment-related grade 3 or higher AEs
8. SAEs by SOC and PT
9. Treatment-related SAEs by SOC and PT
10. AEs leading to permanent treatment discontinuation by SOC and PT
11. AEs leading to dose interruption by SOC and PT
12. AEs leading to on-treatment death by SOC and PT, where AEs leading to death is defined as any event of grade 5 and/or outcome equal to fatal, and on-treatment death is defined as date of death within 30 days of last dose

All TEAEs by SOC/PT and the overall TEAE summary table for the following subgroups will be provided when the numbers of patients are deemed sufficient for the Target mTNBC Population and for the Overall Safety Population:

- Age (<50, 50-65, >65 years)
- Sex (male and female) - only for the Overall Safety Population
- Race
- Ethnicity
- Types of Malignancy according to patient's eligibility criteria CRF - only for the Overall Safety Population
- ECOG Performance Score
- Renal Impairment (creatinine >ULN; creatinine \leq ULN)
- Hepatic Impairment, as defined by baseline serum bilirubin:
 - Normal (\leq ULN)
 - >1 -1.5ULN (> 1 and $\leq 1.5 \times$ ULN)
 - >1.5 ULN ($> 1.5 \times$ ULN)
- UGT1A1 (including but not limited to: *1/*1; *1/*28; *28/*28; not done or missing combined in 1 group)

For the mUC and mBC populations, subgroup analyses of all TEAEs by SOC/PT summary table and the overall TEAE summary table will be done for hepatic impairment and UGT1A1 subgroups, respectively, as defined above.

For the Overall Safety Population, additional subgroup safety analyses including treatment-related AEs and SAEs will be summarized by SOC and PT for hepatic impairment and UGT1A1 subgroups.

In addition to analyses of AEs, adverse events of special interest (AESI) will be assessed. Definitions of AESI, as currently defined, are provided in [Table 6](#), including but not limited to listed. For AESI, frequency tables will be generated, showing overall summary of AESI, Summary of AESI by SOC and PT, Serious AESI by SOC and PT, AESI leading to discontinuation by SOC and PT, AESI leading to treatment interruption by SOC and PT, Grade 3 or higher AESI by SOC and PT, treatment-related AESI (by a worst CTCAE grade of 3, 4, or 5, ≥ 3 and any grade) by SOC and PT. Corresponding listings will also be produced.

Table 6: Definitions of Adverse Events of Special Interest

Adverse event of Special Interest	Definition
Diarrhea	Preferred term: diarrhea
Nausea	Preferred term: nausea
Vomiting	Preferred term: vomiting
Neutropenia+	Preferred terms: neutropenia, neutrophil count decreased, febrile neutropenia
Febrile neutropenia+	Preferred term: febrile neutropenia
Infections	SOC: infections and infestations
Anemia+	Preferred terms: anemia; hemoglobin decreased
Thrombocytopenia+	Preferred terms: thrombocytopenia; platelet count decreased
Fatigue	Preferred term: fatigue and asthenia
Neuropathy+	Preferred term: gait disturbance, hypoesthesia, muscular weakness, neuropathy peripheral, paresthesia, and peripheral sensory neuropathy

Abbreviation: SMQ=Standard MedDRA Query

All definitions based on MedDRA vs 20.0

+ Grouped AE terms

In addition, AESI will be summarized for neutropenia, diarrhea, anemia, nausea and vomiting. For each type of AESI, the following will be generated based on the Overall Safety Population:

- Summary of Subjects with the concerned AESI (by a worst CTCAE grade of 3, 4, or 5, ≥ 3 and any grade)
- Summary of subjects who permanently discontinued treatment due to AESI
- Time to onset of 1st event of AESI from the 1st dose of study drug and of 1st event of AESI or to the 1st event of AESI of Grade 3 or higher; time to onset of event of AESI from the time of the dose that is immediately prior to the onset of the AESI event
- Duration of AESI of any grade, and duration of AESI of grade 3 or higher

Additional analyses of AEs in general or of specific interest, if warranted in the course of safety review, may be generated.

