9.6. Follow-up of Unresolved AEs

All AEs should be followed until they are resolved, or the Investigator assesses them as chronic or stable or the patient's participation in the trial ends (i.e., until a final report is completed for that patient). Instructions for reporting changes in an ongoing AE during a patient's participation in the trial are provided in the instructions that accompany the AE CRFs.

In addition, all AEs and SAEs assessed by the Investigator as possibly related to the investigational medication/product should continue to be followed even after the patient's participation in the trial is over. Such events should be followed until they resolve or until the Investigator assesses them as “chronic” or “stable.” Resolution of such events is to be documented on the appropriate CRF.

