7.2. Death

All-cause deaths will be summarized (including presentation of death due to PD, AE, or other reason) and listed, and deaths within 30 days of the last dose of study drug will be summarized for the Target TNBC Population, mBC Population, mUC Population and Overall Safety Population. In addition, a listing of death based on patient death report CRF will be provided.

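### The fatal adverse event table and listing also require death within 30 days of last dose, so a treatment-emergent event that kills later is missing from both

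*SAP*

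**What the plan says.** SAP Section 7.1 contains two 30-day rules, attached to different dates.

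- **Onset.** TEAEs are "AEs that begin or worsen on or after the start of study drug through 30 days after the last dose of study drug". Only these are summarized.
- **Date of death.** Item 12 in the list of tables is "AEs leading to on-treatment death by SOC and PT". It has two parts: "AEs leading to death is defined as any event of grade 5 and/or outcome equal to fatal", which has no time limit, and "on-treatment death is defined as date of death within 30 days of last dose".

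The fatal-event listing carries the same restriction: "Additional by-patient listings will be provided for AEs leading to on-treatment death, serious AEs (SAEs" and so on. The same sentence adds a listing of "AEs leading to discontinuation of treatment (excluding AEs leading to death", which uses the definition without a time limit.

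SAP Section 7.2 covers deaths as such. All-cause deaths are summarized by reason (progression, AE or other) and listed, and "deaths within 30 days of the last dose of study drug will be summarized".

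Protocol Section 10.3 plans a separate summary, if appropriate, of AEs leading to death. It sets no limit on when the death occurs.

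**The concern.** The onset window already decides whether an event belongs to the treatment period, and the grade or outcome already decides whether it was fatal. The further condition on date of death removes only TEAEs in which the patient took longer to die. Two patients with the same event and the same onset are treated differently according to how long they survived it.

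Safety is a primary objective in both phases of this first-in-man study. Fatal events are likely to be few, so even one omission changes the table that a reader would consult first for fatal toxicity.

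The listings also use mismatched terms. An event that stopped treatment and killed after day 30 is removed from the discontinuation listing because it was fatal, and from the fatal listing because the death was not on treatment.

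**Working it through.** The plan states no figure on this point, so the check applies its selection rules to onset day *t* and death day *d*, both counted from last dose.

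**Rules (SAP 7.1)**

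- TEAE: *t* ≤ 30.
- Table 12 and fatal-event listing: *t* ≤ 30, Grade 5 and/or fatal outcome, and *d* ≤ 30.
- Discontinuation listing: the AE led to discontinuation, and it is neither Grade 5 nor fatal in outcome.

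A TEAE with onset on day *t* is thus counted as fatal only if death follows within 30 − *t* days:

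- onset on day 10: 30 − 10 = 20 days
- onset on day 14, when the final study evaluation takes place (Protocol 6.6): 30 − 14 = 16 days
- onset on day 25: 30 − 25 = 5 days
- onset on day 30: the same day

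**Worked case.** A fatal infection with onset on day 10 that led to permanent discontinuation:

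| Output | Death on day 28 | Death on day 35 |
|---|---|---|
| Meets the TEAE definition | yes | yes |
| Table 12, fatal events by SOC and PT | in | **out** |
| Fatal-event listing | in | **out** |
| Discontinuation listing | out (fatal) | **out (fatal)** |
| Table 10, discontinuation by SOC and PT | in | in |
| Table 8 and SAE listing (a fatal AE is serious, Protocol 9.1) | in | in |
| Table 4, Grade 3 or higher | in if so graded | in if so graded |
| Table 5, Grade 5 column | in if graded 5 | in if graded 5 |
| Special-interest outputs (infections are included) | in | in |
| All-cause death summary and listing (7.2) | in | in |
| Deaths within 30 days (7.2) | in | out |
| Disposition listing, with cause of death (5.1) | in | in |

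In the right-hand column table 10 counts an event that neither the discontinuation listing nor the fatal listing shows, so the table cannot be traced to its natural supporting listing.

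**Does any other table isolate fatal TEAEs?** The serious-event, Grade 3 or higher and discontinuation tables mix fatal with non-fatal events. The 7.2 summary gives the reason for death only in broad classes. The Grade 5 column of table 5 comes closest, but it misses an event recorded as fatal without Grade 5. The SAP's own and/or wording allows for such records. Protocol Table 9, used when no CTCAE criterion exists, ends at Grade 4.

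**Are late deaths known?** Yes. Of AEs possibly related to study drug, Protocol 9.6 says "Such events should be followed until they resolve or until the Investigator assesses them as" chronic or stable. Survival is followed monthly for up to 2 years from final evaluation (Protocol 6.7), and investigators report deaths they learn of at any time (Protocol 9.3).

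**Size.** The documents give no death counts, onset dates or times from onset to death. To show how far the answer depends on such inputs, assume onset spread evenly over days 0 to 14 and an exponential time from onset to death with median *m*, so λ = ln 2 / *m*. The time left to day 30 is then uniform between 16 and 30 days, and the share of fatal TEAEs left out is

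(e^(−16λ) − e^(−30λ)) / (14λ).

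- *m* = 3: (0.0248 − 0.0010) / 3.235 = 0.7%
- *m* = 7: (0.2051 − 0.0513) / 1.386 = 11%
- *m* = 14: (0.4529 − 0.2264) / 0.693 = 33%
- *m* = 21: (0.5897 − 0.3715) / 0.462 = 47%

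The result runs from almost nothing to nearly half on the assumed median alone. It is not an estimate for this trial.

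**The case against.** The best reply has four parts.

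1. **The event is reported elsewhere.** This stands. A reader might infer that late fatal toxicity vanishes from the report. The documents do not support that: the table above shows it in several outputs with no condition on date of death, some of them by preferred term. SAP 7.1 also plans serious, Grade 3 or higher, and treatment-related special-interest tables by SOC and PT, with listings. What is lacking is a single output that isolates all fatal TEAEs.
2. **Table 12 is labelled honestly.** It says on-treatment death and defines the term, and the SAP's version history records that this definition was updated in version 2.0, so it was considered. That answers any charge of concealment. It does not explain why a table of TEAEs needs a second window, or why the two listings use different terms.
3. **The exclusion in the discontinuation listing merely avoids duplication.** That is probably its purpose, and it affects only events that led to discontinuation. It works only if every excluded event appears in the fatal listing, which the 30-day condition prevents.
4. **The shortfall may be zero.** This also stands. A reader might infer that a substantial share of fatal events, or a definite number of patients, will be missing. No figure in the documents supports that. Expected disease progression is not an AE (Protocol Section 9), so late deaths from progression would not add to the count.

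A reader might also infer an unexplained departure from Protocol 10.3. SAP Section 11, which covers changes from the protocol, is redacted, so this cannot be judged.

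**Conclusion.** The point holds as a gap in the dedicated fatal-event outputs. On the text of SAP 7.1, a TEAE with fatal outcome and death more than 30 days after last dose is excluded from table 12 and the fatal-event listing. If it led to discontinuation, it is excluded from that listing as well. This rests only on the written selection rules.

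The direction is certain, since an added condition can only lower the count. The size cannot be determined from the documents and could be nil. The consequence is limited because the event can be recovered from other outputs. This is a low-cost improvement to make, not a failure of safety reporting.

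**What to change.** In SAP 7.1:

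- Define table 12 and its listing as all TEAEs (by onset) with Grade 5 and/or fatal outcome, whatever the date of death.
- Add a column splitting deaths within 30 days from deaths after 30 days of last dose, so that the currently planned count stays visible.
- Exclude from the discontinuation listing only those AEs shown in the fatal listing.

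Keep the 30-day cut for the all-cause death summary in SAP 7.2, where it describes deaths and not events.

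The cost is one changed selection condition, one added column and one reworded exclusion. No new data collection is needed. The downside is that the fatal-event count may be slightly higher.
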